6 HANDLING OF MISSING VALUES

No imputation for missing values will be performed. Missing values will be tabulated in the descriptive tables.

7 STATISTICAL METHODOLOGY AND STATISTICAL ANALYSES

7.1.1 SAMPLE SIZE

Given that this study is purely descriptive in nature and since there are no a priori hypotheses specified, a formal sample size calculation is not applicable. It is anticipated that approximately 600 eligible CAP and cSSTI patients from 35-40 participating sites will be sufficient to conduct this study.

7.1.2 STATISTICAL METHODS

All study outcomes (effectiveness, clinical outcomes, and other endpoints) will be analysed using descriptive statistics to summarize patient and disease characteristics, treatment patterns, and treatment outcomes and health care resource utilisation. Means, standard deviations, medians, minimums and maximums will be provided for continuous variables when performing descriptive analysis of continuous data. Absolute counts and percentages will be provided when performing descriptive analysis of categorical data.

The following variables will be calculated from the information collected in the CRF:

- Body mass index (BMI): Weight(kg) / (Height(cm)*0.01)²
- Geographic region, 2 levels:
 - 1: Europe (France, Greece, Italy, Spain, Russia)
 - 2: Latin America (Brazil, Columbia, Mexico)

Data analyses will be performed separately for the two patient cohorts: CAP and cSSTI. No analyses combining these two patient cohorts will be performed.

Within these patient groups data will be presented in aggregate, as well as stratified by patient and disease characteristics of interest, such as geographic region (see section 4.1.4).

Due to the descriptive nature of the analyses no formal statistical tests will be conducted.. All statistical analyses will be executed using statistical software SAS version 9.4 or later.

7.1.3 STATISTICAL ANALYSES

7.1.4 SPECIFIC APPROACH

Using the endpoints described in section 5.1.6, patient characteristics will be described by summarizing patient demographics at index hospitalization, as well as patient's medical history. CAP-specific characteristics and cSSTI-specific characteristics will also be summarized for each patient cohort respectively. To describe physicians' use of Zinforo® in the clinical management of the patients hospitalized for CAP or cSSTI, details on pre-Zinforo treatment, Zinforo treatment as well as post-Zinforo antibiotic treatment will be summarized to describe line of therapy, monotherapy vs. combination therapy, etc (see related endpoints described in section 5.1.7). Proportion of patients with a clinical response, clinical cure and clinical failure in response to Zinforo® treatment will be summarized. Using the endpoints outlined in section 5.1.3, the clinical outcomes (e.g. hospital readmission, mortality) of patients hospitalized for CAP or cSSTI after starting Zinforo will be summarized and stratified by clinical response. Treatment modification Zinforo® and reasons for treatment modification will be described for the CAP and cSSTI patient cohorts, using the endpoints collected as described in section 5.1.4. Healthcare resource utilization will be described for patients hospitalized for CAP or cSSTI after starting Zinforo® and stratified by clinical response, using the appropriate endpoints as described in section 5.1.8.

7.1.5 INTERIM ANALYSIS

One interim analysis will be performed on all validated and locked patient data within the EDC. The time frame for the interim database lock and interim analysis will be based on Pfizer's internal needs and dissemination plans. The interim analysis will be performed on the full set of planned analyses. Due to the purely descriptive nature of the study no further considerations on issues such as alpha spending are required. The final analyses will be performed after completion of data collection and subsequent data base lock.

8 LIST OF TABLES AND TABLE SHELLS

8.1.1 ANALYSES OF PATIENTS WITH CAP

8.1.2 CHARACTERISTICS OF PATIENTS WITH CAP

Table 1. Demographic characteristics of included CAP patients at index hospitalization

CAP Demographic characteristics	All CAP patients (N=XX)	
	n	%
Age		
<90 years		
≥ 90 years		
If <90 years,		
Mean (SD)		
Median (Min Max)		
<65 years		
≥ 65 years		
Sex		
Male		
Female		
Race, Ethnicity		
White, Caucasian		
Black/African-American/Caribbean		
Latin-American		
Asian		
Middle Eastern		
Mixed		
Other		
Not available		
Country		
France		
Greece		
Italy		
Spain		
Russia		
Brazil		
Columbia		
Mexico		

PFIZER CONFIDENTIAL

CCI

CAP Demographic characteristics	All CAP patients (N=XX)	
	n	%
Height (cm)		
Mean (SD)		
Median (Min-Max)		
Unknown		
Weight (kg)		
Mean (SD)		
Median (Min-Max)		
Unknown		
BMI		
Mean (SD)		
Median (Min-Max)		
Unknown		
Type of residence/cohabitation (pre index if changed after discharge)		
Nursing home or extended care facility		
Living independently		
Living with care support (family, friend, hired support)		
Other		
Unknown		
Smoking habits		
Non-smoker		
Ex-smoker (stopped \geq 365 days ago)		
Occasional smoker (less than 1 tobacco product per day)		
Habitual smoker (1 or more tobacco products per day)		
Unknown		

Abbreviations: n=number; SD = Standard deviation

PFIZER CONFIDENTIAL

CCI

Table 2. Medical history in patients with CAP

Medical history	All CAP patients (N=XX)	
	n	%
Medical condition(s) at index hospitalization		
None		
AIDS/HIV infection		
If HIV infected: Controlled with HAART		
Yes (n, % of HIV infected)		
No (n, % of HIV infected)		
Unknown (n, % of HIV infected)		
Alcohol abuse		
Cancer/malignancy		
Cerebrovascular disease		
Chronic dialysis within the past 30 days		
Chronic obstructive pulmonary disease		
Chronic renal disease		
Congestive heart failure		
Decompensated cirrhosis		
Diabetes mellitus		
Immunosuppressive disease		
Influenza		
Injection drug use		
End stage liver disease		
Peripheral vascular disease		
Respiratory disease		
Other relevant condition(s) or disease(s) requiring chronic drug treatment.		
Unknown		

Abbreviations: AIDS/ HIV: acquired immunodeficiency syndrome/ human immunodeficiency virus, HAART: highly active antiretroviral therapy

Table 3. Hospitalization and treatments in the 3 months prior to index hospitalization in patients with CAP

Prior hospitalization	All CAP patients (N=XX)
	n %
Hospitalization for any reason in the 3 months before index hospitalization	
Yes	
No	
Unknown	
If hospitalized	
Duration of hospitalization previous to index	
Mean (SD)	
Median (Min-Max)	
Invasive major surgical treatment in the 3 months before index	
Yes	
No	
Unknown	
Therapies received in the 3 months before index	
Antimicrobial (e.g. antibiotics, antivirals)	
Immunosuppressors/ immunomodulators	
Anticoagulants	
Non-steroid anti-inflammatory agents (NSAIs)	
Home infusion therapy	
Home wound care provided by a medical professional	
None	

Abbreviations: Max: maximum; Min: minimum; SD: standard deviation.

PFIZER CONFIDENTIAL

CCI

Table 4. Diagnostics in patients with CAP

CAP Diagnostic	All CAP patients (N=XX)	
	n	%
Radiographic findings in tests for CAP		
Infiltrate		
Consolidation		
Pleural effusion		
Other findings		
Unknown		
None of the above		
Triggering signs and symptoms at CAP diagnosis		
New or increased cough		
Purulent sputum or change in sputum character		
Auscultatory findings consistent with pneumonia		
Dyspnea, tachypnea, or hypoxemia (O2 saturation < 90% on room air or pO2 < 60 mmHg)		
Fever (>38 °C oral; > 38.5 °C rectally or tympanically) or hypothermia (< 35 °C)		
WBC count > 10,000 cells/mm ³ or < 4,500 cells/mm ³		
Unknown		
None of the above		
Criteria for severe CAP		
Yes		
No		
Unknown		
Prognostic scoring system used		
PORT Score / Pneumonia Severity Index		
Mean (SD)		
Median (Min-Max)		
CURB-65		
Mean (SD)		
Median (Min-Max)		
Other		
None		
Unknown		

Abbreviations: Max: maximum; Min: minimum; SD: standard deviation. O2: oxygen, pO2: oxygen partial pressure, WBC: white blood cells, PORT: Pneumonia Severity Index, CURB-65: Confusion, Blood urea, Respiratory rate, Blood pressure, age ≥ 65

Table 5. Diagnosis and infection details in patients with CAP

CAP Time of infection	All CAP patients (N=XX)	
	n	%
Time of CAP diagnosis		
Prior to index hospitalization		
Days prior to index hospitalization		
Mean (SD)		
Median (Min-Max)		
During index hospitalization		
Unknown		
Recurrent CAP infection		
Yes		
No		
Unknown		

Abbreviations: Max: maximum; Min: minimum; SD: standard deviation.

PFIZER CONFIDENTIAL

CCI

Table 6. Microbiological findings in patients with CAP

CAP Microbiological findings	All CAP patients (N=XX)	
	n	%
Microbiological CAP diagnosis positive for		
Streptococcus pneumonia		
Multidrug resistant S. pneumoniae		
Penicillin resistant S. pneumoniae		
Escherichia coli		
Mycoplasma pneumonia		
Chlamydophila pneumonia		
Haemophilus influenza		
H. Parainfluenzae		
Legionella spp.		
Staphylococcus aureus		
Methicillin resistance Staphylococcus aureus		
Methicillin susceptible S. aureus		
Gram-negative bacilli		
Moraxella catarrhalis		
Coxiella burnetii		
Klebsiella pneumonia		
Other enterobacteria		
Pseudomonas aeruginosa		
Aspirative pneumonia		
Other microorganism		
Unknown		
None of the above		
Investigation conducted for positive microbiological CAP diagnosis		
Sputum examination		
Blood culture		
Bronchoalveolar lavage or bronchial brush examination		
Pleural fluid sample examination		
Legionella antigen test in urine		
Pneumococcal antigen test in urine		
Other		
Unknown		
None of the above		

Table 7. Additional tests and vaccination status in patients with CAP

CAP test and vaccination	All CAP patients (N=XX)	
	n	%
PCF determination of H1N1 influence virus performed		
Yes		
No		
Unknown		
If yes:		
Positive		
Negative		
Influenza vaccination received within the 12 months pre index hospitalization		
Yes		
No		
Unknown		
Pneumococcal vaccination received		
Yes		
No		
Unknown		
Biomarkers used to monitor the clinical evolution of the patient		
CRP		
Procalcitonin		
Other biomarker		
Unknown		
None of the above		

Abbreviation: CRP: c-reactive protein

PFIZER CONFIDENTIAL

CCI

8.1.3 HEALTHCARE RESOURCE USE FOR PATIENTS WITH CAP STARTING ZINFORO

Table 8. Utilization during index hospitalization in patients with CAP

Resource utilization	All CAP patients (N=XX)
	n %
Duration of index hospitalization (days)	
Mean (SD)	
Median (Min-Max)	
Duration of days in ICU	
Mean (SD)	
Median (Min-Max)	
Quick sepsis-related organ failure assessment (qSOFA) conducted	
Yes	
No	
Unknown	
If qSOFA was conducted (n, % of qSOFA assessed)	
Glasgow coma scale <15	
Systolic blood pressure <100 mmHg	
High respiration rate (\geq 22 breaths per minute)	
Patient required isolation	
Yes	
No	
Unknown	
If patient isolated:	
Duration of isolation (days)	
Mean (SD)	
Median (Min-Max)	
Unknown	

Abbreviations: ICU: intensive care unit; Max: maximum; Min: minimum; qSOFA: Quick sepsis-related organ failure assessment; SD: standard deviation.

Table 9. Hospitalisation cost in patients with CAP

Hospital Cost	All CAP patients (N=XX)	
	n	%
Hospital Cost - standard hospital (local currency)		
Mean (SD)		
Median (Min-Max)		
Hospital Cost - advanced level (local currency)		
Mean (SD)		
Median (Min-Max)		
Hospital Cost - standard hospital (USD)		
Mean (SD)		
Median (Min-Max)		
Hospital Cost - advanced level (USD)		
Mean (SD)		
Median (Min-Max)		

Abbreviations: USD: US Dollars, Max: maximum; Min: minimum; SD: standard deviation.

Table 10. Utilization during index hospitalization by response status in patients with CAP

Resource utilization	CAP responders (N=XX)		CAP non- responders (N=XX)	
	n	%	n	%
Duration of index hospitalization (days)				
Mean (SD)				
Median (Min-Max)				
Duration of days in ICU				
Mean (SD)				
Median (Min-Max)				
Quick sepsis-related organ failure assessment (qSOFA) conducted				
Yes				
No				
Unknown				
If qSOFA was conducted (n, % of qSOFA assessed)				
Glasgow coma scale <15				
Systolic blood pressure <100 mmHg				
High respiration rate (\geq 22 breaths per minute)				
Patient required isolation				
Yes				
No				
Unknown				
If patient isolated:				
Duration of isolation (days)				
Mean (SD)				
Median (Min-Max)				
Unknown				

PFIZER CONFIDENTIAL

CCI

Table 11. Hospitalisation cost by response status in patients with CAP

Hospital Cost	CAP responders (N=XX)		CAP non- responders (N=XX)	
	n	%	n	%
Hospital Cost- standard hospital (local currency)				
Mean (SD)				
Median (Min-Max)				
Hospital Cost- advanced level (local currency)				
Mean (SD)				
Median (Min-Max)				
Hospital Cost- standard hospital (USD)				
Mean (SD)				
Median (Min-Max)				
Hospital Cost- advanced level (USD)				
Mean (SD)				
Median (Min-Max)				

Abbreviations: USD: US Dollars, Max: maximum; Min: minimum; SD: standard deviation.

Table 12. Ventilation and parenteral nutrition in patients with CAP

Ventilation and parenteral nutrition	All CAP patients (N=XX)	
	n	%
Patient required mechanical ventilation		
Yes		
No		
Unknown		
If patient received ventilation:		
Type of ventilation		
Invasive ventilation (n, % ventilated)		
Duration of invasive ventilation (days)		
Mean (SD)		
Median (Min-Max)		
Non-invasive ventilation (n, % ventilated)		
Duration of non-invasive ventilation (days)		
Mean (SD)		
Median (Min-Max)		
Including high flow oxygen therapy		
Yes (n, % ventilated)		
No (n, % ventilated)		
Unknown (n, % ventilated)		
Patient received parenteral nutrition		
Yes		
No		
Unknown		
If Yes:		
Duration of parenteral nutrition (days)		
Mean (SD)		
Median (Min-Max)		
Unknown		

Abbreviations: Max: maximum; Min: minimum; SD: standard deviation.

Table 13. Treatments received during index hospitalization in patients with CAP

Treatments received	All CAP patients (N=XX)	
	n	%
Treatment received during index hospitalization?		
Surgery related to the infection		
Surgery unrelated to the infection		
Blood pressure support		
If blood pressure support received:		
Fluid resuscitation (n,% blood pressure support)		
Vasopressors (n,% blood pressure support)		
Invasive procedures (n,% blood pressure support)		
Unknown		
Other		
None of the above		

PFIZER CONFIDENTIAL

CCI

Table 14. Complications during index hospitalization in patients with CAP

Complications	All CAP patients (N=XX)
	n %
Renal failure necessitating renal replacement	
Yes	
No	
Unknown	
If renal replacement :	
Duration of therapy (days)	
Mean (SD)	
Median (Min-Max)	
Renal replacement after first dose of Zinforo	
Yes (n, % with renal replacement)	
No (n, % with renal replacement)	
Unknown (n, % with renal replacement)	
Serum creatinine at the first Zinforo dose (mg/dL)	
Mean (SD)	
Median (Min-Max)	
Unknown	
Complications developed during index hospitalization	
Sepsis	
Severe sepsis	
Septic shock	
Unknown	
None of the above	

Abbreviations: Max: maximum; Min: minimum; SD: standard deviation.

Table 15. Dosages of Zinforo and other antibiotics in patients with CAP

Complications	All CAP patients (N=XX)
	n %
Total number of doses of Zinforo administered	
Mean (SD)	
Median (Min-Max)	
Total number doses of other antibiotics administered in combination with Zinforo	
Mean (SD)	
Median (Min-Max)	
Total number of doses of other antibiotics administered post Zinforo treatment	
Mean (SD)	
Median (Min-Max)	

Abbreviations: Max: maximum; Min: minimum; SD: standard deviation.

PFIZER CONFIDENTIAL

CCI

Table 16. Resource use post index hospitalization in patients with CAP

Resource utilization post index	All CAP patients (N=XX)	
	n	%
Home-based care received through a health-care agency (e.g. for wounds, intravenous infusions)		
Yes		
No		
Unknown		
If home based care received ,		
Duration of home-based care (days)		
Mean (SD)		
Median (Min-Max)		
Re-hospitalized within 30 days of initial discharge		
Yes		
No		
Unknown		
If re-hospitalized ,		
Number of re-hospitalizations		
Mean (SD)		
Median (Min-Max)		
Duration of all hospitalizations		
Mean (SD)		
Median (Min-Max)		
Admission reason:		
For index infection (n,% of re-hospitalizations)		
For other reason (n,% of re-hospitalizations)		
Unknown (n,% of re-hospitalizations)		

Abbreviations: Max: maximum; Min: minimum; SD: standard deviation.

PFIZER CONFIDENTIAL

CCI

8.1.4 PHYSICIANS USE OF ZINFORO® (AND OTHER ANTIBIOTICS) DURING INDEX HOSPITALIZATION IN PATIENTS WITH CAP

Table 17. Pre Zinforo treatment- Summary across all treatment lines in patients with CAP

Antibiotic treatment pre Zinforo	All CAP patients (N=XX)
	n %
Antibiotic treatment for the index infection received prior to Zinforo	
Yes	
No	
Pre Zinforo treatment received	
Aminoglycoside	
Betalactam	
Carbapenem	
Ceftriaxone	
Cephalosporins	
Glycopeptide	
Macrolide	
Betalactam	
/Combination	
Quinolone	
Sulfonamide	
Clindamycin	
Linezolid	
Other antibiotic agent	
Unknown	
Line of therapy	
First	
Second	
Third	
Fourth	
Number of pre Zinforo lines of therapy	
Mean (SD)	
Median (Min-Max)	
Route of administration	
Oral	
Intra-venous	
Intra-muscular	
Subcutaneous	
Unknown	

PFIZER CONFIDENTIAL

CCI

Antibiotic treatment pre Zinforo	All CAP patients (N=XX)	
	n	%
Duration of pre Zinforo treatment (days)		
Mean (SD)		
Median (Min-Max)		
Treatment type		
Empiric		
Definitive/Specific		
Unknown		
Number of administrations		
Mean (SD)		
Median (Min-Max)		
Number of doses administered		
Mean (SD)		
Median (Min-Max)		
Administration location		
ICU		
General ward		
At home		
Out patient		
Medical setting		
Unknown		
Treatment modification		
Yes		
No		
Unknown		
If yes:		
Time to treatment modification from initial dose		
Reason for treatment modification		
Treatment response		
Time to clinical response		
Clinical failure details		
Daily dose unit		

Abbreviations: Max: maximum; Min: minimum; SD: standard deviation.

Table 18. Pre Zinforo treatment by line of treatment in patients with CAP

Pre Zinforo treatment	Line of treatment			
	1st Line N, %	2nd Line N, %	3rd Line N, %	4th Line N, %
Aminoglycoside				
Betalactam				
Carbapenem				
Ceftriaxone				
Cephalosporins				
Glycopeptide				
Macrolide				
Betalactam /Combination				
Quinolone				
Sulfonamide				
Clindamycin				
Linezolid				
Other antibiotic agent				
Unknown				

PFIZER CONFIDENTIAL

CCI

Table 19. Zinforo treatment during index hospitalization in patients with CAP

Zinforo treatment	All CAP patients (N=XX)	
	n	%
Zinforo line of therapy		
First		
Second		
Third		
Fourth		
Duration of Zinforo treatment (days)		
Mean (SD)		
Median (Min-Max)		
Unknown		
Time from admission to 1st dose (days)		
Mean (SD)		
Median (Min-Max)		
Unknown		
Time from symptom onset to 1st dose (days)		
Mean (SD)		
Median (Min-Max)		
Unknown		
Treatment type		
Empiric		
Definitive/Specific		
Unknown		
Daily dose (mg/kg)		
Mean (SD)		
Median (Min-Max)		
Number of infusions per day		
Mean (SD)		
Median (Min-Max)		
Unknown		
Administration location		
ICU		
General ward		
At home		
Out-patient setting		
Medical clinic		
Unknown		

Abbreviations: ICU: intensive care unit; Max: maximum; Min: minimum; SD: standard deviation.

PFIZER CONFIDENTIAL

CCI

Table 20. Zinforo administered in combination therapy in patients with CAP

Antibiotic treatments given in combination with Zinforo	All CAP patients (N=XX)	
	n	%
Zinforo as Mono/ Combination treatment		
Monotherapy		
Combination therapy		
Unknown		
If administered in combination:		
Antibiotic treatment received		
Aminoglycoside		
Betalactam		
Carbapenem		
Ceftriaxone		
Cephalosporins		
Glycopeptide		
Macrolide		
Betalactam		
/Combination		
Quinolone		
Sulfonamide		
Clindamycin		
Linezolid		
Other antibiotic agent		
Unknown		
Route of administration		
Oral		
Intra-venous		
Intra-muscular		
Subcutaneous		
Unknown		
Duration of combination treatment (days)		
Mean (SD)		
Median (Min-Max)		
Unknown		
Number of doses administered		
Mean (SD)		
Median (Min-Max)		
Unknown		

Abbreviations: Max: maximum; Min: minimum; SD: standard deviation.

PFIZER CONFIDENTIAL

CCI

Table 21. Zinforo treatment and concomitant therapy in patients with CAP

Therapies concomitant to Zinforo	All CAP patients (N=XX)	
	n	%
Concomitant therapy given		
Yes		
No		
If concomitant therapy "yes"		
Therapy received		
Immunosuppressors/ Immunomodulators		
Anticoagulants		
Non-steroidal anti-inflammatory agents (NSAIs)		
Chemotherapeutic agents		
Other		
Unknown		

PFIZER CONFIDENTIAL

CCI

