Rational and background:	
cSSTI represents a major clinical problem^{1,2,3} and is associated with considerable morbidity, mortality, resource use and healthcare costs.⁴⁻⁹ Current treatment options are compromised by resistance and tolerability issues. CAP is a common respiratory illness¹⁰⁻¹⁶ that is also associated with considerable morbidity, mortality,^{15,17,18} resource use and healthcare costs.^{11,14,18,19}
 
In patients with CAP and cSSTI (particularly those at risk of treatment failure), there is a need for an alternative treatment option that will improve empiric treatment success rates by providing activity against a range of suspected causative pathogens (including MRSA and S. pneumoniae) combined with a good tolerability profile.
 
Ceftaroline fosamil (Zinforo®) is a novel 5th generation cephalosporin with rapid bactericidal action against a broad range of common Gram positive and Gram negative pathogens. Zinforo® is approved in the EU in adults and children from the age of two (2) months for the treatment of complicated skin and soft tissue infections (cSSTI) and community-acquired pneumonia (CAP).
 
For the treatment of cSSTI and CAP, the recommended dose of Zinforo® is 600 mg administered every 12 hours by intravenous infusion over 60 minutes (standard dose). For the treatment of adult patients with cSSTI confirmed or suspected to be caused by S. aureus with a Minimum Inhibitory Concentration (MIC) = 2 mg/L or 4 mg/L to ceftaroline, the dose of Zinforo® is 600 mg administered every 8 hours by intravenous infusion over 120 minutes (high dose). The recommended treatment duration for cSSTI is 5 to 14 days and the recommended duration of treatment for CAP is 5 to 7 days.
 
Zinforo® is an effective treatment for patients hospitalised with CAP or cSSTI, including those at risk of treatment failure and/or with intolerance/contraindications to commonly-used antibiotics.^{20,29, 30-32, 33} At present, the real-world use and effectiveness of Zinforo® in treating patients hospitalized with CAP and cSTTI has not been evaluated in a usual care setting in Europe and Latin America.

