 - Microbiological Diagnosis (investigations or diagnostic tests performed, positive microbiological diagnosis obtained, microorganism name, bacteremia diagnosed, the pathogen(s), source(s), and the specimen collection date(s). Pathogens identified by blood, respiratory (eg, sputum, bronchoalveolar lavage), or pleural effusion cultures will be recorded for patients with bacterial pneumonia. Pathogens identified by blood or skin/soft tissue/bone/wound cultures will be recorded for patients with cSSTIs. Minimum inhibitory concentrations (MIC) of antibacterial drugs for pathogens isolated from samples collected within one week before the start of treatment through 24 hours after discontinuation of Zinforo® will be recorded:
 - MIC of ceftaroline for all isolated pathogens;
 - MIC of oxacillin, vancomycin, linezolid, and daptomycin for *S. aureus*;
 - MIC of ceftriaxone for MSSA;
 - MIC of penicillin and ceftriaxone for *S. pneumoniae*.

- Zinforo® Treatment (treatment duration, line of therapy, time from hospital admission to first dose, time from symptom onset to first dose, empiric vs. definitive therapy, monotherapy vs. combination therapy, dose, number of infusions per day, number of doses administered, ICU vs. general medical ward administration, reason for switch to Zinforo® if not 1st line treatment).
- Pre-Zinforo® IV Antibiotic Treatments for the index infection (each monotherapy/combination antibiotic therapy name, line of therapy, route of administration, duration of treatment, time from admission to first dose, time from symptom onset to first dose, empiric vs. definitive therapy, daily dose, number of doses administered, treatment response, time to treatment modification from initial dose (days), reason for treatment modification, ICU vs. general medical ward administration).
- Concurrent IV antibiotic treatments administered with Zinforo® for index infection (antibiotic therapy name, route of administration, treatment duration, daily dose, number of doses administered).
- Post-Zinforo® antibiotic treatments for index infection (antibiotic therapy name, route of administration, treatment duration, daily dose, number of doses administered, reason for switch, treatment response, ICU vs. general medical ward administration).

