5.1.7 PHYSICIANS' USE OF ZINFORO® DURING INDEX HOSPITALIZATION

- Pre Zinforo® treatment
 - Antibiotic class
 - Line of therapy
 - Route of administration
 - Duration of treatment Time from admission to 1st dose
 - Time from symptom onset to 1st dose
 - Treatment type
 - Daily dose
 - Treatment modified (Reason)
 - Treatment response/ failure
 - Time to clinical response / failure
 - Clinical failure details
- Zinforo® treatment
 - Duration of treatment
 - Time from admission to 1st dose
 - Time from symptom onset to 1st dose
 - Treatment type
 - Daily dose
 - Number of infusions per day
 - Administration location
 - Zinforo® as monotherapy/ combination (including further details of combination therapy)
 - Concomitant therapy
- Post Zinforo® antibiotic treatment
 - Generic name of treatment
 - Line of therapy
 - Route of administration
 - Time from Zinforo® discontinuation to initiation of new treatment
 - Daily dose
 - Number of doses administered
 - Administration location
 - Reason for switch to this treatment:
 - Treatment response
 - Clinical cure achieved?
 - Clinical failure details

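### Zinforo daily dose is tabulated in mg/kg and infusions per day only by mean and median, so Table 46 (and Table 19) shows no direct count of patients by fixed-dose regimen

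*SAP*

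**What the plan says.** The protocol abstract describes the standard regimen, for both infections, as "600 mg administered every 12 hours by intravenous infusion over 60 minutes (standard dose". It describes a second regimen as "600 mg administered every 8 hours by intravenous infusion over 120 minutes (high dose". The second is introduced with the words "For the treatment of adult patients with cSSTI confirmed or suspected to be caused by" *S. aureus* with a ceftaroline MIC of 2 or 4 mg/L, so it is described for part of the adult cSSTI population and not for CAP. Protocol section 7 repeats both descriptions. Neither is expressed per kilogram.

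Among the Zinforo treatment variables, protocol 9.3 lists "dose, number of infusions per day, number of doses administered".

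SAP 5.1.7 lists daily dose with no unit, and separately "Number of infusions per day". The unit first appears in the shells: Table 19 (SAP 8.1.4, CAP) and Table 46 (SAP 8.1.11, cSSTI) both carry the row "Daily dose (mg/kg" with mean (SD) and median (min-max) and no unknown line. In both tables infusions per day has the same summaries plus an unknown line. Tables 15 and 42 add only the total number of doses.

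SAP 7.1.2 names BMI and geographic region as variables calculated from the CRF; a weight-based dose is not among them. SAP section 6 rules out imputation and says missing values will be tabulated. Tables 1 and 29 have an unknown line for weight.

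**The concern.** The drug is described in fixed milligrams, so the natural description of its use is milligrams per day and the number of patients on each schedule. The shells give neither. A daily dose per kilogram varies with body weight even when every patient has the same prescription, and it can take the same value under different prescriptions. If it is computed from recorded weight, it also loses patients whose weight is unknown, and the row has nowhere to show how many.

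Infusions per day would normally take a few whole-number values, yet it is treated as continuous. What is at stake is how clearly the report describes dosing in the cSSTI cohort, where the protocol describes two regimens. In the CAP cohort it describes one, so there the matter is the unsuitable scale and the visibility of any other schedule that was used.

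**Working it through.** The plan states no figure on this point, so there is nothing of its own to reproduce. The dosing inputs come from the protocol abstract. The body weights are assumptions, because the documents give no weight distribution.

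**1. Daily dose in mg.** Daily dose = 600 × 24 / interval in hours.
- Every 12 hours: 600 × 24 / 12 = 1,200 mg, two infusions.
- Every 8 hours: 600 × 24 / 8 = 1,800 mg, three infusions.
- Ratio: 1,800 / 1,200 = 1.5. In mg the two values are distinct and need no weight.

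**2. The same doses in mg/kg.** The values coincide whenever weights differ by a factor of 1.5. For illustration, 1,200 / 60 = 1,800 / 90 = 20 mg/kg, and 1,200 / 80 = 1,800 / 120 = 15 mg/kg. Over an assumed 50 to 120 kg:

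| Regimen | At 120 kg | At 50 kg |
|---|---|---|
| 1,200 mg/day | 10 mg/kg | 24 mg/kg |
| 1,800 mg/day | 15 mg/kg | 36 mg/kg |

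The ranges overlap from 15 to 24 mg/kg.

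**3. How much the overlap matters for individual patients.** I simulated 400,000 normally distributed weights, limited to 40-160 kg, with an equal mix of the two regimens, and took the single mg/kg cut that best separates them.

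| Assumed weight, mean (SD) | Best cut | Misclassified |
|---|---|---|
| 75 (10) kg | 19.6 mg/kg | about 6% |
| 75 (15) kg | 19.3 mg/kg | about 15% |
| 80 (20) kg | 17.8 mg/kg | about 20% |

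**4. The pooled mean in mg/kg.** To second order, the mean of 1/weight is (1/m)(1 + s²/m²), for mean weight m and SD s. Take s = 15 kg.
- m = 70, nobody on the high regimen: 1,200 × (1/70)(1 + 225/4,900) = 17.9 mg/kg.
- m = 80, 30% on the high regimen: mean dose 0.7 × 1,200 + 0.3 × 1,800 = 1,380 mg, and 1,380 × (1/80)(1 + 225/6,400) = 17.9 mg/kg.

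Simulation gives the same two values. One reported mean thus fits 0% or 30% on the high regimen.

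**5. Infusions per day.** If a share p has three and all others exactly two, the mean is 2 + p and the SD is √(p(1 − p)). A mean of 2.2 with SD 0.40 then implies p = 20%. With a share q on one per day, the mean is 2 + p − q and SD² = p + q − (p − q)²:
- p = 25%, q = 5%: mean 2.2, SD √(0.30 − 0.04) = 0.51.
- p = 30%, q = 10%: mean 2.2, SD √(0.40 − 0.04) = 0.60.

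The mean alone no longer gives p. A reader who knew that only one, two and three occur could still solve for p from the mean and SD, but the row does not say which values occur. With four values even the full row is not enough. Shares of 5, 70, 20 and 5% at one to four per day, and shares of 7, 64, 26 and 3%, both give mean 2.25, SD √(5.45 − 2.25²) = 0.62, median 2 and range 1-4. The share on three per day is 20% in one and 26% in the other.

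**6. A related inconsistency.** Protocol 9.9 justifies the four-dose entry rule by saying the drug is given twice daily, so that four doses mean at least two days: 4 × 12 = 48 hours. Under the every-8-hours description, 4 × 8 = 32 hours. These passages do not agree.

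**The case against.** The strongest reply is that little is lost. The study is descriptive and tests no hypothesis. No estimate of response, failure or resource use depends on these rows, and the sponsor could add a count later from data already collected. If only two and three infusions per day occur, the existing row yields the regimen share exactly, and a maximum of three already shows that some three-a-day use took place. All of this stands, and it keeps the point minor.

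It is also true that the SAP nowhere writes a conversion from mg to mg/kg. The label may be a unit on the CRF, which is not among the documents, or a slip in the shells. The loss of patients with unknown weight is therefore conditional on the figure being derived from weight. The mismatch between a per-kilogram label, a fixed-mg description and an unlabelled variable in SAP 5.1.7 does not depend on how it arose.

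Two stronger readings are tempting, and the documents do not support them. A reader might infer that Objective 2 cannot be met. But the objective spells out its content as line of therapy, monotherapy or combination, and empiric or definitive use, and Tables 19-20 and 46-47 report all of these as counts and percentages. A reader might also infer that response ought to be shown by regimen. No objective asks for that, and SAP 4.1.4 does not list regimen as a covariate. Because the high regimen is described for *S. aureus* at particular MICs, such a comparison would be confounded by indication.

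**Conclusion.** The point holds as a minor reporting defect. It bears mainly on Table 46, because only the cSSTI population has two regimens described; in Table 19 it concerns the scale and any use outside the one regimen described.

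The mg/kg row does not reliably distinguish 1,200 from 1,800 mg/day. The size of that problem, an overlap at 15-24 mg/kg and roughly 6 to 20% misclassified, rests on assumed weights and, for the percentages, on an assumed equal mix. It would be unsupported to say that the tables cannot separate the regimens at all: infusions per day does so when only two and three occur. It stops doing so when an unknown set of other frequencies is present, and it never shows the mg per infusion. Sample size and error rates are unaffected, and nothing here judges either regimen.

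**What to change.** In Tables 46 and 19:
- Report daily dose in mg.
- Add n (%) by infusions per day (2, 3, other, unknown).
- Add n (%) by mg per infusion, with an unknown line.
- If mg/kg is kept as an extra row, define its derivation in SAP 7.1.2, including which weight is used, and add an unknown line.

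Give the daily dose in SAP 5.1.7 its unit. Reconcile the twice-daily statement in protocol 9.9 with the every-8-hours description in the abstract and section 7; which wording should stand is for the sponsor to settle.

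The cost is a few shell rows and one definition, using variables protocol 9.3 already lists. No new data collection or change in study size is needed.
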